11.5.2 Secondary Efficacy Analyses

Secondary efficacy analyses will be performed using the mITT analysis set. For all secondary endpoints, the summary statistics or frequency tables will be created by treatment group for each week or scheduled visit. The secondary endpoints for each DS-5565 arm will be compared with that for placebo with no adjustment of multiple comparisons.

11.5.2.1 Responder Rate for Averaged Daily Pain Score

ADPS responder rate, defined as the proportion of subjects with $\geq 30\%$, and $\geq 50\%$ reduction from baseline to Week 14, will be calculated by treatment group. ADPS responder rate of each arm of DS-5565 will be compared with that of placebo using logistic regression model. The cumulative distribution of reduction from baseline in ADPS will be provided as a continuous responder analysis¹⁵.

11.5.2.2 Short-Form McGill Pain Questionnaire

For the sensory score, affective score, total score, VAS, and the present pain intensity index, the measured value and the change from baseline will be summarized at each scheduled visit. The change from baseline in the parameters above will be compared between each arm of DS-5565 and placebo.

11.5.2.3 Modified Brief Pain Inventory (Short Form)

For the parameters related to severity of pain and impact on daily functions, the measured value and the change from baseline will be summarized at each scheduled visit. The change from baseline in the parameters above will be compared between each arm of DS-5565 and placebo.

11.5.2.4 Patient Global Impression of Change

PGIC score (1 to 7 on a 7-point scale) will be described as frequency table and will be compared between each arm of DS-5565 and placebo.

11.5.2.5 Sleep-Interference Score

The summary statistics will be computed for the ADSIS and their change from baseline at each week. The change from baseline in sleep interference score will be compared between each arm of DS-5565 and placebo.

11.5.2.6 Medical Outcomes Study Sleep Scale

For the subscales of sleep disturbance, snoring, awakening short of breath or with a headache, somnolence, sleep adequacy, sleep problems index, and quantity of sleep, the measured value and the change from baseline will be summarized at each scheduled visit. The change from baseline in the subscales above will be compared between each arm of DS-5565 and placebo.

For the optimal sleep which is dichotomized version of optimal sleep findings, the summary will be provided as frequency tables and the parameter will be compared between treatments.

11.5.2.7 Hospital Anxiety and Depression Scale

For the subscales of anxiety and depression, the measured value and the change from baseline will be summarized at baseline and Visit 10. The change from baseline in the subscales above will be compared between each arm of DS-5565 and placebo.

11.5.2.8 SF-36

For the eight-scale profile of physical functioning, role-physical, bodily pain, general perception of health, vitality, social functioning, role-emotional, and mental health, the transformed score and their change from baseline will be described as summary statistics

at each scheduled visit. The change from baseline will be compared between each arm of DS-5565 and placebo for each scale profile above.

11.5.2.9 Evaluation of Symptoms

The evaluation of symptoms (four categories of “improved”, “no change”, “worse”, “no symptoms”) will be described as frequency table and will be compared between each arm of DS-5565 and placebo.

11.6 Pharmacokinetic/Biomarker Analyses

11.6.1 Pharmacokinetic Analyses

Scatter plot illustrating the pharmacokinetic relationship between time after dose and plasma concentration by treatment for each visit will be created, using the PK analysis set. The population PK analysis will be reported separately from the clinical study report (i.e. not in the clinical study report).

11.6.2 Biomarker Analyses

Not applicable.

11.7 Safety Analyses

All safety analyses will be performed on a by-treatment basis, unless otherwise specified, using the safety analysis set.

11.7.1 Adverse Event Analyses

Any AEs that appear after the first administration, or that worsen relative to the pre-treatment state, are considered as TEAEs. TEAEs will be coded using the Medical Dictionary for Regulatory Activities (MedDRA).

The number and percentage of subjects reporting TEAEs will be calculated for the categories listed below by treatment and all-DS-5565 treatment. The number and percentage of subjects reporting TEAEs and ADRs will be summarized by system organ class, preferred term, and treatment and all-DS-5565 treatment.

- TEAE
- ADR
- Serious TEAE
- Serious ADR

- Severe TEAE
- Severe ADR
- Significant TEAE
- Significant ADR
- TEAE leading to treatment discontinuation
- ADR leading to treatment discontinuation

Time to first TEAE, defined as the duration from first administration of investigational product to the first TEAE, will be summarized based on the Kaplan-Meier product limit method by treatment and all-DS-5565 treatment.

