5.1.2 Dosing Regimens for the Study

The duration of investigational product administration will be 14 weeks, consisting of a titration period and a fixed-dose period. As Table 5-1 shows, the treatment period will begin at bedtime on Day 1 (Visit 2) and will continue until the morning of Day 99 (Visit 10). During the treatment period, 1 tablet either DS-5565 or matching placebo will be administered orally twice daily (in the morning and at bedtime). The subject must select the administration timing, either fasted or fed in the morning at randomization

(Visit 2), and it will be followed during the treatment period.

Table 5-1 Method of Administration During the Treatment Period

Group	Day 1		Day 2 to 7		Day 8		Day 9 to 14		Day 15		Day 16 to 98		Day 99	
	Morni ng	Bedti me	Morni ng	Bedti me	Morni ng	Bedti me	Morni ng	Bedti me	Morni ng	Bedti me	Morni ng	Bedti me	Morni ng	Bedti me
DS-5565 15 mg QD	—	5	0	5	0	10	0	10	0	15	0	15	0	—
DS-5565 10 mg BID	—	5	5	5	5	10	10	10	10	10	10	10	10	—
DS-5565 15 mg BID	—	5	5	5	5	10	10	10	10	15	15	15	15	—
Placebo	—	0	0	0	0	0	0	0	0	0	0	0	0	—

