6.5 Post-treatment Follow-up (Visit 11, 7 days after the completion of administration)

Follow-up observations will be conducted 7 days after the completion of administration (Visit 11). The following activities and/or examinations will be performed at post-treatment follow-up. No follow-up observation is required for subjects enrolled in an open-label extension study.

- Complete HADS
- Measure body weight
- Perform physical examination
- Perform abbreviated neurological examination
- Measure blood pressure and pulse rate
- Collect blood and urine samples for laboratory tests
- Evaluate AEs
- Complete C-SSRS
- Record and evaluate concomitant drugs and concomitant therapy

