9.1 Adverse Events

9.1.1 Definition of Adverse Event

An AE is any unfavorable and unintended sign (including an abnormal laboratory value or abnormal vital sign), symptom, or disease that develops after the subject signs the Informed Consent Form (ICF) and up to 7 days after the last dose of study medication (Visit 11), regardless of relationship to the investigational product.

Any symptom that the investigator or sub-investigator considers associated with DPN will be evaluated as an efficacy variable and will not be regarded as an AE. However, if the symptom is considered potentially related to the investigational product, such symptom will be regarded as an AE. If any pre-existing symptom or disease is aggravated during the study period, the aggravation will be reported as an AE, and the date of confirming the aggravation will be considered the date of event onset.

Dizziness, somnolence, edema, and weight increase are currently defined as “significant AEs”. Any other significant AEs to be added will be specified in the statistical analysis plan (SAP).

All antiepileptic drugs carry a risk of increased suicidal behavior and ideation. Furthermore, increased hepatic transaminases have been observed in the DS-5565 development program. Therefore, the following “suicidal behavior and ideation” and “liver enzyme elevations/liver dysfunction” will be treated as adverse events of special interest.

- Increase in ALT or AST ≥ 5 x ULN
- ALT or AST rises to ≥ 3 x ULN and persists for more than 2 weeks
- Concurrent increases in ALT or AST ≥ 3 x ULN and T-Bil ≥ 2 x ULN
- ALT or AST ≥ 3 x ULN associated with a clinical presentation suggestive of liver injury (ie, including the appearance of fatigue, nausea, vomiting, jaundice, right upper quadrant pain or tenderness, fever, rash, and/or eosinophilia)
- Serious hepatobiliary adverse event
- Severe hepatobiliary adverse event

- Hepatobiliary Adverse event leading to Discontinuation
- Any transaminase elevation associated with a clinical presentation suggestive of Liver injury
- An elevation of ALT or AST $\geq 3 \times$ ULN (without clinical presentation suggestive of liver injury)
- AE related to suicide (if there are any “yes” responses to any of the questions in the C-SSRS)

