6. STUDY PROCEDURES

A study visit schedule in tabular format is provided in section 17.1.

In principle, all of the activities and/or examinations will be recorded with the date in the CRF.

6.1 Visit 10

At the beginning of the titration period, the following activities and/or examinations will be performed and 5 mg BID of new investigational product will be issued to the patient. However, if the same examinations are already performed at Visit 10 of the double-blind study, those data will be used.

- Obtain written informed consent
- Evaluate inclusion criteria and exclusion criteria
- Complete SF-MPQ
- Complete HADS
- Measure body weight
- Perform physical examination
- Perform evaluation of edema
- Perform ophthalmologic examination
- Measure blood pressure and pulse rate
- Perform 12-lead ECG
- Collect blood and urine samples for laboratory tests
- Collect blood sample for evaluation of fasting blood glucose levels
- Collect blood sample for evaluation of HbA1c
- Evaluate AEs
- Complete C-SSRS
- Perform pregnancy test (only in women of childbearing potential)
- Evaluate prior drug treatment, concomitant drugs, and concomitant therapy
- Issue the investigational product

6.2 Visit 11

After the first 2 weeks of the titration period (starting at Visit 10), the subject will come to the study site (Visit 11). At Visit 11, the following activities and/or examinations will be performed and 10 mg BID of new investigational product will be issued to the patient after the investigator or sub-investigator confirms tolerability and reviews continuation of

the treatment.

- Complete SF-MPQ
- Complete HADS
- Measure body weight
- Measure blood pressure and pulse rate
- Perform evaluation of edema
- Perform neurological examination
- Collect blood and urine samples for laboratory tests
- Evaluate AEs
- Complete C-SSRS
- Record and evaluate concomitant drugs and concomitant therapy
- Issue the investigational product
- Collect unused investigational product, and record the date of the first dose taken and review drug-taking compliance

6.3 Visit 12

Two weeks after Visit 11, the subject will come to the study site (Visit 12). The following activities and/or examinations will be performed at Visit 12. At this point, 10 mg BID or 15 mg BID of new investigational product will be issued to the patient after the investigator or sub-investigator confirms tolerability and reviews continuation of the treatment.

- Complete SF-MPQ
- Complete HADS
- Measure body weight

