9.1 Adverse Events

9.1.1 Definition of Adverse Event

An AE is any unfavorable and unintended sign (including an abnormal laboratory value or abnormal vital sign), symptom, or disease that develops from Visit 10 to 7 days after the last dose of study medication (Visit 25), regardless of relationship to the investigational product.

Any symptom that the investigator or sub-investigator considers associated with DPN will be evaluated as an efficacy variable and will not be regarded as an AE. However, if the symptom is considered potentially related to the investigational product, such a symptom will be regarded as an AE. If any pre-existing symptom or disease is aggravated during the study period, the aggravation will be reported as an AE, and the date of confirming the aggravation will be considered the date of event onset.

Dizziness, somnolence, edema, and weight increase are currently defined as significant AEs. Any other significant AEs to be added will be specified in the statistical analysis plan (SAP).

All antiepileptic drugs carry a risk of increased suicidal behavior and ideation. Furthermore, increased hepatic transaminases have been observed in the DS-5565 development program. Therefore, the following “suicidal behavior and ideation” and “liver enzyme elevations/liver dysfunction” will be treated as adverse events of special interest.

- Increase in ALT or AST ≥ 5 x ULN
- ALT or AST rises to ≥ 3 x ULN and persists for more than 2 weeks
- Concurrent increases in ALT or AST ≥ 3 x ULN and T-Bil ≥ 2 x ULN
- ALT or AST ≥ 3 x ULN associated with a clinical presentation suggestive of liver injury (ie, including the appearance of fatigue, nausea, vomiting, jaundice, right upper quadrant pain or tenderness, fever, rash, and/or eosinophilia)
- Serious hepatobiliary adverse event

- Severe hepatobiliary adverse event
- Hepatobiliary Adverse event leading to Discontinuation
- Any transaminase elevation associated with a clinical presentation suggestive of Liver injury
- An elevation of ALT or AST $\geq 3 \times$ ULN (without clinical presentation suggestive of liver injury)
- AE related to suicide (if there are any “yes” responses to any of the questions in the C-SSRS)

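### For subjects who enter the extension, the double-blind AE/TEAE window is not closed at the first open-label dose, so first-exposure reactions in former placebo subjects could be counted under placebo

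*Combined protocol and SAP*

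**What the plan says.** **Double-blind part.** Section 9.1.1 counts an event as an AE "up to 7 days after the last dose of study medication (Visit 11), regardless of relationship to the investigational product". Section 11.7.1 adds the treatment-emergent rule: "Any AEs that appear after the first administration, or that worsen relative to the pre-treatment state, are considered as TEAEs". That rule has no end date of its own. Section 11.7 states that "All safety analyses will be performed on a by-treatment basis". Section 5.1.2 says that dosing "will continue until the morning of Day 99 (Visit 10"). Section 6.5 waives the follow-up visit for rollovers: "No follow-up observation is required for subjects enrolled in an open-label extension study". Sections 3.1.2 and 3.1.4 repeat the waiver. None of the three says that the AE window is shortened.

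**Extension.** Section 6.1 provides that at Visit 10 "5 mg BID of new investigational product will be issued to the patient". Section 3.1.2 places the 5 mg BID titration directly after the double-blind treatment period and describes no gap. Section 9.1.1 of the extension opens its own window, for an event that "develops from Visit 10 to 7 days after the last dose of study medication (Visit 25"). Section 11.7.1 of the extension starts its TEAEs at the first open-label dose. It does not say that such events leave the double-blind tables.

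**The concern.** For a subject who rolls over, the seven days after the last double-blind dose are also the first seven days on open-label DS-5565. An event in that week meets both definitions of an AE and both definitions of a TEAE. In the double-blind tables it would appear under the randomised arm.

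For a former placebo subject this is the first contact with the drug. Section 9.1.1 classes dizziness and somnolence as significant AEs, Section 1.3 names them as anticipated risks, and Section 11.7.1 gives significant TEAEs and ADRs their own rows. If reactions of this kind enter the placebo column, the randomised comparison moves towards no difference for the terms where a difference is most expected. Time to first TEAE is exposed in the same way, because no censoring rule is given at the switch.

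**Working it through.** The plan states no figure on this point, so there is none to reproduce. The check compares the windows by study day and then shows what the overlap could mean under stated assumptions.

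**1. Windows on the nominal schedule**

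| Item | Source | Study day |
|---|---|---|
| Last double-blind dose | 5.1.2 | Day 99, morning (Visit 10) |
| End of double-blind AE window | 9.1.1 | Day 99 + 7 = Day 106 |
| End of double-blind TEAE rule | 11.7.1 | none stated |
| Open-label DS-5565 issued | Extension 6.1 | Day 99 (Visit 10) |
| Start of extension AE window | Extension 9.1.1 | Day 99 (Visit 10) |
| Start of extension TEAEs | Extension 11.7.1 | first open-label dose |

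The overlap is essentially the whole of Day 99 to Day 106. The Visit 11 label in the double-blind definition does not settle the matter. Rollovers have no double-blind Visit 11, and in the extension that number belongs to the visit after two weeks of open-label dosing.

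**2. Number of placebo subjects affected**

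Inputs: up to about 400 enter the extension (extension Section 11.11); allocation is 2:1:1:1 with 300 on placebo (Section 11.11). Assumption: rollover is proportional to allocation.

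- Placebo rollovers = 400 × 2/5 = 160.
- Share of the placebo arm = 160 / 300 = 53%.

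**3. Effect on one drug-specific term**

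The documents give no first-week reaction rate. Let q be an assumed net rate, that is, the excess over background, between 2% and 10%. Added points = 160 × q / 300.

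| q | Added placebo subjects | Added points |
|---|---|---|
| 2% | 3.2 | 1.1 |
| 5% | 8 | 2.7 |
| 10% | 16 | 5.3 |

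These are upper values for each q, because a subject who already had the term on double-blind treatment is not counted again. With a 5% earlier rate for the term, the additions are (160/300) × 0.95 × q, or 1.0, 2.5 and 5.1 points. If placebo rollovers number 120 to 200 instead of 160, the range without this correction is 0.8 points (120 × 2% / 300) to 6.7 points (200 × 10% / 300).

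**4. Why the any-TEAE rate is not a measure of this**

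The Asian Phase 2 study (Section 1.1.1.5.2) reports any TEAE in 48.9% at 5 mg BID and 53.4% on placebo. Its primary endpoint was at Week 7. Assuming a constant hazard over those 7 weeks:

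- 5 mg BID: −ln(1 − 0.489)/7 = 0.096 per week, so 1 − exp(−0.096) = 9.1% in one week.
- Placebo: −ln(1 − 0.534)/7 = 0.109 per week, so 1 − exp(−0.109) = 10.3% in one week.

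On these figures an off-drug follow-up week would collect as many events of any kind as a week at 5 mg BID. Extra any-TEAEs in the overlap week are therefore consistent with background and do not show a drug effect.

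**The case against.** The strongest reply is that the documents, read together, already point to Visit 10 as the handover. Rollovers have no double-blind follow-up visit, they give separate consent at Visit 10 (extension Section 4.1), and the extension starts its own AE and TEAE counts there. Section 11.2 also leaves detailed methods to a SAP to be written before unblinding, and a cut-off for the TEAE flag would naturally sit in it. This stands as far as it goes: the intention is probably a handover, and the unseen SAP may state one. But starting one window does not close the other, and the wording in Sections 9.1.1 and 11.7.1 keeps these events in the double-blind count.

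A second reply is that every DS-5565 arm also carries the extra open-label week. That is right, and it makes the net bias smaller than a gross count of placebo events. It does not cancel the bias, because only former placebo subjects are newly exposed.

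A reader might go further and infer a size from the Asian Phase 2 rates of somnolence (14.7%) and dizziness (11.0%). The documents do not support that. Those rates are pooled over all DS-5565 doses, no placebo rates for these terms are given to subtract, and nothing says what share of such events begins in the first week. Nor do the documents show that misattribution will in fact occur; they show only that the rule as written allows it.

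Finally, the consequence is limited. The AE tables are descriptive, no efficacy result depends on them, and the time-to-first-TEAE curve changes only in its last week. Reporting one event in both parts does not by itself bias the extension's summary.

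**Conclusion.** The concern holds as a gap in the rule. For subjects who enter the extension, the double-blind AE and TEAE definitions overlap the first week of open-label DS-5565, and no section removes those events from the double-blind by-treatment tables. Applied literally, first-exposure reactions in former placebo subjects could be counted under placebo, biasing drug-specific terms and ADRs towards no difference.

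The size cannot be estimated from the documents. The illustration of at most about 1 to 5 points for a given term rests on two assumptions: proportional rollover (160 of 300 placebo subjects) and a net first-week reaction rate of 2% to 10%. It is the gross addition to the placebo column, so any rise in the DS-5565 arms would offset part of it. No claim is made that the overall any-TEAE rate is distorted. If the separate SAP already ends the window at the first open-label dose, only the protocol wording needs to be brought into line.

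**What to change.** Add to Sections 9.1.1 and 11.7.1 of the double-blind part, and carry into the SAP before unblinding:

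*For subjects who enter the open-label extension, the double-blind AE/TEAE period ends immediately before the first open-label dose. Events with onset or worsening after that point are counted in the extension only. Time to first TEAE is censored at the same point.*

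Table 9-1 records the date of AE onset and no clock time, so the SAP should also fix one convention for events dated on the day of the first open-label dose. Extension Section 6.2 already records the date of that dose.

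The cost is one sentence and a date condition in the TEAE flag; no visit, dosing or data collection changes. The small downside is that rollovers have less follow-up after their last double-blind dose than other subjects, which cannot be avoided once they take open-label drug.

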11.7.2 Clinical Laboratory Evaluation Analyses

For the hematology and blood chemistry test parameters, summary statistics will be calculated for the measured values and change from baseline at each scheduled visit. A shift table will be created based on the categories of “abnormal low”, “normal”, and “abnormal high” between baseline and each scheduled visit.

Additionally, for ALT, AST, T-Bil, and ALP, the number and percentage of subjects who meet the criteria specified in Food Drug Administration (FDA) Drug-Induced Liver Injury (DILI) guideline¹⁶ and evaluation of drug-induced serious hepatotoxicity (e-DISH) plot will be provided. For the urinalysis parameters excepting specific gravity, the number and percentage of subjects will be provided at each visit. Summary statistics will be tabulated for the specific gravity. A shift table will be created based on the categories of “normal” and “abnormal” between baseline and each scheduled visit.

11.7.3 Vital Sign Analyses

Summary statistics will be calculated for measured values and changes from baseline in the supine and orthostatic blood pressure, and supine pulse rate at each scheduled visit.

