1.3 Risks and Benefits for Study Subjects

The results from nonclinical studies suggest that subjects treated with DS-5565 may experience improvement in DPNP, post-herpetic neuralgia (PHN), and fibromyalgia (FM). The clinical efficacy of DS-5565 has been evaluated in 2 Phase 2, multi-center, randomized, double-blind, placebo- and active-comparator controlled adaptive study in subjects with DPNP. In DS5565-A-U201 conducted in the US, DS-5565 15 mg QD, 10 mg BID, and 15 mg BID treatment groups demonstrated statistically significant mean reductions in ADPS from baseline to end-of-treatment compared to placebo. In DS5565-A-J202 conducted in Asian countries, DS-5565 5 mg BID, 10 mg BID, and 15 mg BID showed numerically mean reductions in ADPS, although the reduction was not statistically significant. These data provide proof-of-concept for DS-5565 as a treatment for DPNP and suggest that DS-5565 may have utility in other chronic pain conditions such as PHN and FM.

Anticipated risks of DS-5565 include the occurrence of adverse reactions related to CNS depression, such as dizziness and somnolence, as well as peripheral edema. Other notable TEAEs that have been observed in Phase 1 and Phase 2 studies include elevations of hepatic transaminases and suicide. For the approved $\alpha_2\delta$ ligands, in addition to dizziness, somnolence, and peripheral edema, certain adverse reactions requiring caution have also been reported, including but not limited to: weight gain, ophthalmologic disorders, suicidal behavior and ideation, angioedema, hypersensitivity, abrupt or rapid discontinuation, abuse potential, congestive heart failure, renal failure, and creatine kinase elevations.

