9.5 Vital Signs

Vital signs will be recorded at all visits and will include supine pulse rate and supine and orthostatic blood pressure. For measurement of supine blood pressure, subjects should be in a supine or semirecumbent position for at least 5 minutes before the blood pressure measurement. Measurement of orthostatic blood pressure should follow measurement of supine blood pressure. Subjects should be asked to stand for 3 minutes before measurement of orthostatic blood pressure. Measurement of blood pressure should be conducted using a calibrated manometer or automatic inflatable cuff monitor; the blood pressure cuff should be kept in place between supine and orthostatic blood pressure measurements. Results will be recorded in the CRF.

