11.2 General Statistical Considerations

The statistical package SAS[®] (Version 9.2 or higher) will be used to produce tables, figures, and listings.

The modified intent-to-treat (mITT) analysis set will be used as a primary efficacy analysis set for all efficacy analyses and the per-protocol set (PPS) will be used for sensitivity analysis. All safety analyses and pharmacokinetic analyses will be conducted for the safety analysis set and PK analysis set, respectively.

The primary imputation will be based on “nonfuture dependence” model using the pattern mixture approach under the missing not at random (MNAR) mechanism for the missing weekly ADPS data¹⁹⁻²¹. Reason for dropout together with the time of dropout will be used for constructing the missing data pattern. Detail will be at Section 11.5.1 and in the SAP.

Raw data will be presented to the exact precision at which they were collected.

For summary statistics, means and medians will be displayed to one more decimal place than was determined for raw data, dispersion statistics will have two more decimal places, and the minimum and maximum will be displayed to the same number of decimal places as the raw data.

Quantitative data will be tabulated with descriptive summary statistics: arithmetic mean, standard deviation (SD), median, minimum and maximum values, and number of observations. For categorical data, frequency tables will be provided.

All hypothesis testing will provide the *P* values and their corresponding two-sided 95% confidence intervals if applicable. The significance level is 0.05 (two-sided) for all hypothesis testing. The type I error rate will be controlled at less than 0.05 for the multiple comparisons of the primary endpoint of ADPS at Week 14 between each DS-5565 arm (15 mg QD, 10 mg BID, or 15 mg BID) and placebo, using combination approach of Bonferroni-Holm method and gate-keeping procedure (see Section 11.5.1). No adjustment for multiple comparisons will be made for the secondary efficacy analyses.

Analysis for the change from baseline, including the shift table, will be conducted for the

subjects who have an available baseline value and at least one post-randomization value. Subgroup analyses by country (eg, Japan, Korea, and Taiwan) will be conducted for some of efficacy and safety analyses specified in the SAP.

PK analysis will be detailed in the PK analysis plan (PAP).

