11.7.3 Vital Sign Analyses

Summary statistics will be calculated for measured values and changes from baseline in the supine and orthostatic blood pressure, and supine pulse rate at each scheduled visit.

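### Supine and standing blood pressure are taken as a pair at every visit, but the planned vital-sign tables summarise each position separately and show neither the within-subject change on standing nor how many subjects had a fall

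*Combined protocol and SAP*

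**What the plan says.** Section 9.5 (double-blind protocol) states: "Vital signs will be recorded at all visits and will include supine pulse rate and supine and orthostatic blood pressure". The supine reading comes after at least 5 minutes lying or semirecumbent. For the second reading, "Measurement of orthostatic blood pressure should follow measurement of supine blood pressure" and "Subjects should be asked to stand for 3 minutes before measurement of orthostatic blood pressure", with the cuff left on between the two. In this protocol, then, orthostatic blood pressure is the standing reading itself, not a difference. Section 9.5 of the open-label extension sets the same procedure.

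Section 11.7.3 plans: "Summary statistics will be calculated for measured values and changes from baseline in the supine and orthostatic blood pressure", together with supine pulse rate, at each scheduled visit. Section 11.7.3 of the extension uses the same wording. Section 11.2 defines the summary for quantitative data as "arithmetic mean, standard deviation (SD), median, minimum and maximum values, and number of observations".

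On the risk side, 1.3 states: "Anticipated risks of DS-5565 include the occurrence of adverse reactions related to CNS depression, such as dizziness and somnolence". Section 9.1.1 adds "Dizziness, somnolence, edema, and weight increase are currently defined as" significant AEs. Dizziness was reported in 9.4% of DS-5565 subjects in the US Phase 2 study and 11.0% in the Asian one (1.1.1.5).

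**The concern.** Taking two readings in a fixed order, minutes apart, on one arm with the cuff in place is how one obtains a change on standing within a subject. The plan collects that pair and then analyses the two halves apart. The change from baseline in 11.7.3 is a change over time within one position, not a change between positions.

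A secondary objective is to characterise safety and tolerability, and dizziness is both an anticipated risk and a significant AE. Whether subjects who report dizziness, or subjects on DS-5565 generally, have larger falls on standing than placebo subjects is a question these data could answer and the planned tables cannot. Other safety data are treated differently: 11.7.2 gives laboratory tests shift tables and gives liver tests counts of subjects meeting set criteria, and 11.7.4 gives the ECG a shift table. Blood pressure has no subject-level count.

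**Working it through.** The documents give no figure for blood pressure, so there is nothing to reproduce. The check is first textual and then an illustration.

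**1. What the planned tables contain.** For each arm, visit and position: mean, SD, median, minimum, maximum and n, for the value and for its change from baseline. If the same subjects contribute both readings, the mean fall is recoverable as mean supine minus mean standing. Its SD is not, because

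SD(fall) = sqrt(SD_sup² + SD_st² − 2 × r × SD_sup × SD_st),

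and the correlation r between the positions is not reported. The minimum and maximum describe single positions. A low standing minimum may belong to a subject who was equally low when supine, and neither extreme gives a count.

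**2. How much is left open.** Assumptions: supine 135 (SD 15), standing 132 (SD 16), bivariate normal, cut-off 20 mm Hg. The mean fall is 135 − 132 = 3, and the share falling by at least 20 is 1 − Φ((20 − 3)/SD(fall)).

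| r | SD(fall), mm Hg | Share falling ≥ 20 mm Hg |
|---|---|---|
| 0.9 | 7.0 | 0.8% |
| 0.8 | 9.8 | 4.2% |
| 0.7 | 12.0 | 7.9% |
| 0.6 | 13.9 | 11.1% |
| 0.5 | 15.5 | 13.7% |

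Every row has the same mean and SD in each position.

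**3. How little a minority moves the mean.** Section 11.11 plans 300 placebo subjects and 150 per DS-5565 arm, so the standard error of a difference in means is SD × sqrt(1/150 + 1/300) = 0.1 × SD. Suppose 5% of one active arm (0.05 × 150 = 7.5, so 7 or 8 subjects) has an extra 25 mm Hg standing fall and nobody on placebo does. Mean standing pressure moves by 0.05 × 25 = 1.25 mm Hg. For an SD of 10, 12 or 15 this is z = 1.25, 1.04 or 0.83.

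Now let some placebo subjects fall too. The shift in the mean is the difference in shares times the size of the fall (20 to 30 mm Hg), with a standing SD of 12 to 18. Power for means is Φ(shift/(0.1 × SD) − 1.96). Power for proportions uses the usual two-sided 0.05 comparison with pooled variance under the null.

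| Placebo vs active | Mean shift, mm Hg | Power, means | Power, proportions |
|---|---|---|---|
| 5% vs 10% | 1.0–1.5 | 8–24% | 52% |
| 5% vs 15% | 2.0–3.0 | 20–71% | 93% |
| 10% vs 20% | 2.0–3.0 | 20–71% | 82% |

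No test of vital signs is planned. Power serves here only as a yardstick for how plainly each summary would show the same difference. It treats a single visit and assumes that fallers are classified without error.

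**The case against.** Several points on the other side stand.

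- A reader might infer that the plan reports two means and nothing else. It does not. Section 11.2 adds SD, median, minimum and maximum, and 11.7.3 applies these to changes from baseline as well, so the largest drop over time in standing pressure appears for each arm and visit. What is missing is the paired change and a count.
- A reader might infer that a postural fall would go unseen. The AE definition in 9.1.1 includes abnormal vital signs, 11.7.1 tabulates TEAEs by preferred term and counts significant TEAEs, dizziness among them, and a DSMB reviews unblinded safety data (11.9). This route is real but incomplete. No blood pressure criterion is given. Section 9.4 says that clinically significant laboratory changes should be regarded as AEs, while 9.5 says only that results go in the CRF. Section 9.1.2 directs general questioning without prompting for specific symptoms.
- A reader might infer that DS-5565 is suspected of lowering standing pressure. The documents do not say so. Section 1.3 ties dizziness to CNS depression, and no postural fall appears among the anticipated risks there, the significant AEs or the AEs of special interest. Section 9.5 gives no reason for the paired reading, so its purpose is inferred from the procedure.
- Section 11.2 announces a detailed SAP before unblinding (before database lock for the extension), which may define such a variable. The available text contains no SAP wording on vital signs, so one can say only that the plan as written does not include it.
- The readings are kept in the CRF, so the difference could still be derived later, though then without a cut-off fixed before unblinding.

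**Conclusion.** The point holds as a low-cost improvement, not as a fault that endangers a conclusion of the trial. As written, the vital-sign tables cannot show the spread of the within-subject change on standing or the number of subjects with a fall, and detection rests on investigator judgement and volunteered symptoms. That follows from the text of 9.5, 11.2 and 11.7.3 and needs no assumption.

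The size does need assumptions. The range of 0.8% to 13.7%, the mean shifts of 1.0 to 3.0 mm Hg and the power figures all rest on pressures, SDs, correlations, shares and a cut-off that the documents do not supply. They show the direction of the loss, not its amount in this trial.

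The contrast with placebo applies to the double-blind study only. It should not be carried over to the extension, which is open-label with flexible dosing and no randomised arms. There the gap is purely descriptive. No efficacy conclusion is touched.

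**What to change.** In 11.7.3 of the double-blind study, derive standing minus supine pressure, systolic and diastolic, for each subject and visit. Summarise this variable and its change from baseline by arm with the statistics already listed in 11.2. Add the number and percentage of subjects whose fall exceeds a cut-off, by visit and at any post-baseline visit. The sponsor should choose the cut-off and fix it in the SAP before unblinding; the 20 mm Hg used above is only a working assumption. The by-visit figures matter because subjects who leave early have fewer visits at which a fall can be seen.

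In 11.7.3 of the extension, report the same variable descriptively for the single group, without a placebo contrast.

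The cost is one derived variable and one table in each study, with no new measurement. Section 11.2 requires an amendment only where a change alters the principal features of the protocol, so an entry in the SAP would probably be enough.
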